# List of abbreviations and definition of terms

ADaM	Analysis data model
AE	Adverse event
BID	Twice daily
BMI	Body mass index
CDISC	Clinical Data Interchange Standards Consortium
CI	Confidence interval
eCRF	Electronic case report form
ECG	Electrocardiogram
EOT	End-of-text
EQ5D	EuroQol-5 Domain Questionnaire
ICOAP	Intermittent and Constant Osteoarthritis Pain
IMP	Investigational medicinal product
ITT	Intention-to-treat
LK	Likert
MedDRA	Medical Dictionary for Regulatory Activities
MMRM	Mixed model repeated measures
mITT	Modified intention-to-treat
N/A	Not applicable
NRS	Numerical rating scale
OA	Osteoarthritis
OMERACT-	The Osteoarthritis Research Society International (OMERACT) Standing Committee
OARSI	for Clinical Trials Response Criteria Initiative and the Outcome Measures in
	Rheumatology (OARSI) committee
PGA	Patient Global Assessment
PP	Per-protocol
PT	Preferred term
Q1	First quartile
Q3	Third quartile
QD	Once daily
QoL	Quality of life
Randomized	Subject randomized to study treatment
SAE	Serious adverse event
SAF	Safety analysis set
SAP	Statistical analysis plan
Screened	Subject who enters the screening phase of the study
SD	Standard deviation
SDTM	Study data tabulation model
SE	Standard error
SOC	System organ class
TLF	Tables, listings and figures
VAS	Visual analog scale
WHO	World Health Organisation
WOMAC	Western Ontario and McMaster Universities Osteoarthritis Index
WPAI	Work and Productivity and Activity Index

# 1 Introduction

This document describes the planned statistical analyses and data presentations for study AMZ001-006 as outlined in protocol version 1.2 dated 22NOV2018.

### 1.1 Study objectives and endpoints

### 1.1.1 Objectives

The primary objective of this study is:

• To evaluate the change in pain intensity, in terms of the WOMAC pain score of the target knee

The secondary objectives of this study are:

- To evaluate changes in symptoms of OA
- To evaluate the changes in physical functioning
- To evaluate administration regimens of AMZ001
- To evaluate the safety and tolerability of AMZ001
- To evaluate changes in quality of life

#### 1.1.2 Endpoints

The primary endpoint of this study (double-blind treatment groups only) is:

• The change from baseline in WOMAC pain sub-score (questions 1 to 5) in the target knee as evaluated at week 4.

The secondary endpoints of this study (double-blind treatment groups only) are:

- Changes from baseline in WOMAC total score and the WOMAC function and stiffness scores at week 4
- Changes from baseline in constant and intermittent OA pain assessed by ICOAP scores at week 4
- Changes from baseline in WOMAC pain weight-bearing score (questions 1, 2, and 5) and non-weight bearing score (questions 3 and 4) at week 4
- Changes from baseline in physical function assessed by the chair-stand test at week 4
- OMERACT-OARSI responder rate at week 4
- Total dose of rescue medication calculated as the sum of tablets used, based on pill counts
- Time between baseline and first use of rescue medication
- Changes from baseline in WOMAC pain sub-score (questions 1 to 5) between groups receiving AMZ001 QD and BID in the target knee as evaluated at week 4

- Changes from baseline in constant and intermittent OA pain assessed by ICOAP scores between groups receiving AMZ001 QD and BID at week 4
- Changes from baseline in WOMAC pain weight-bearing score (questions 1, 2, and 5) and non-weight bearing score (questions 3 and 4) between groups receiving AMZ001 QD and BID at week 4
- Changes from baseline in physical function assessed by the chair-stand test between AMZ001 QD and BID at week 4
- Changes from baseline in WOMAC total score and the WOMAC function and stiffness scores between AMZ001 QD and BID at week 4.
- Changes from baseline in the impact of OA on daily living as assessed by the PGA score at week 4
- Changes from baseline in work productivity and activity assessed by the WPAI at week 4
- Changes from baseline in quality of life assessed by the EQ5D at week 4

The safety endpoints of this study are:

- Nature, incidence and severity of AEs
- Changes in laboratory safety parameters, vital signs, 12-lead ECG parameters and weight
- Nature, incidence and severity of skin reactions on the application site

# 2 Study design

The trial is a multi-center, double-blind, randomized, placebo-controlled trial of AMZ001 for the treatment of knee osteoarthritis symptoms. The trial also includes a single-blind component, consisting of Voltaren® 1 % gel. The purpose of the trial is to evaluate the efficacy, safety and tolerability of once or twice daily application of AMZ001 during a 28-day period in subjects with radiographic and symptomatic knee osteoarthritis in either one or both knees.

A total of approximately 440 subjects are planned to be randomized. The subjects will be randomized in a ratio of 3:3:3:2 with approximately 120 subjects in each of the three doubleblinded treatment groups (AMZ001 BID, AMZ001 QD and placebo) and approximately 80 subjects in the single-blinded treatment group (comparator Voltaren® gel 1 %).

The trial consists of three phases: screening, treatment, and follow-up, as illustrated in Table 1.

# 2.1 Overview of study procedures

#### Table 1 Overview of study procedures

				On Treatment Visits			14-Day	
								Follow-up 
	Screening	Screening	Baseline					(± 5 days)
Activity/Assessment	1a 	1b 	V2	V3	V4	V5	V6	V7
Study Week	-	-	0	1	2	3	4	6
Study Day	-21 to - 5	-13 to -1	1	8	15	22	29	43
Visit Window (days)	-	-	0	+/- 2	+/- 2	+/- 2	+/- 2	+/- 5
Informed Consent	Х							
Medical history	Х							
Inclusion/exclusion criteria	х	Х	х					
Demographic data	Х							
Physical examination	Х						Х	
Skin Tolerability Assessment			X 	х	х	х	х	
Knee X-ray (both knees)	Х							
Instructions on reporting pain 	х							
WOMAC Questionnaire 5,6,7		Х	X5	х	х	х	х	
ICOAP Questionnaire 6			Х	Х	Х	Х	Х	
Pain Diary 			X8	X8	X8	X 	X8	
Patient Global Assessment			x	х	х	х	х	
WPAI			Х	Х	Х		Х	
EQ5D			Х			Х	Х	
Satisfaction questionnaire					х		x	
Chair-stand test 			Х		Х		Х	
Selection of target knee			Х					

				On Treatment Visits			14-Day	
Activity/Assessment	Screening 1a 	Screening 1b 	Baseline V2	V3	V4	V5	V6	Safety Follow-up  (± 5 days) V7
Study Week	-	-	0	1	2	3	4	6
Study Day	-21 to - 5	-13 to -1	1	8	15	22	29	43
Height and weight	Х						X9	
Blood pressure and heart rate	х		х	Х	х	х	х	
Adverse events	X 	Х	Х	Х	Х	Х	Х	Х
Concomitant medication	Х	Х	Х	Х	Х	Х	Х	Х
Randomization			Х					
Study drug dispensation and weighing of kit(s)			х		X 			
Dispensation of IMP "instructions for use" pamphlet			х		x			
Instruction of study drug application and frequency of use			х					
Application of morning study drug on site under staff supervision			х	х	×	х	х	
Weighing of kit(s) for compliance assessment				Х	х	х	х	
Rescue medication dispense			х		(X) 	(X) 		
Rescue medication collection 					(X) 	(X) 	х	
12 lead ECG	Х						Х	
(Rescue) Analgesic Wash-out		х	Х	Х	x	х	х	
Hematology	Х			Х	Х	Х	Х	
Safety chemistry and urine dipstick	Х			Х	х	Х	х	
Pregnancy test 	Х		Х		Х		Х	
Blood sample for plasma level of diclofenac 					х		х	

EQ5D: EuroQol-5 Domain. ICOAP: Intermittent and Constant Osteoarthritis Pain. WOMAC: The Western Ontario and McMaster Universities Osteoarthritis Index. WPAI: Work Productivity Activity Index.

- 1. If subject is washed out of analgesics at Screening Visit 1a, the examinations scheduled for screening visits 1a and 1b can be performed on the same day.
- 2. Phone call.
- 3. Skin assessment to be performed prior to application of study drug at baseline visit.
- 4. Subjects will be educated on appropriate expectations around their participation in a clinical study and the importance of reliably consistently and accurately reporting their pain throughout the study.
- 5. WOMAC pain sub-score (5 questions) to be assessed on a daily basis on paper at home during first week of treatment, i.e. the period between Visit 2 and Visit 3.
- 6. Assessed without analgesic medication for five half-lives of the analgesic.
- 7. WOMAC assessment of hips should only be performed at the screening visit.

- 8. To be completed daily in the evening during the first week of treatment, i.e. between Visit 2 and Visit 3). In the period between other subsequent visits, the questionnaire will be completed during the evening of the day prior to the next visit.
- 9. Only weight collected.
- 10. Conditions previously unknown to the subject at the time of the screening visit will be recorded as medical history. All subsequent events will be recorded as adverse events.
- 11. To be collected/dispensed if previously dispensed supply of rescue medication was depleted and empty packaging returned to site.
- 12. Collection of remaining rescue medication at Visit 6. Empty packaging of previously dispensed kit should be returned to the site if new rescue medication is requested.
- 13. Serum test at screening visit, urine dipstick at all other visits.
- 14. To be done after IMP application and questionnaire/test completion (approximately 1-2 hours after IMP application). Exact time of IMP application and time of blood sampling must be documented.
- 15. Dispensation is not mandatory for subjects allocated to Voltaren® gel

### 2.2 Determination of sample size

The power is determined from expected changes in the primary endpoint of the change from baseline in pain as evaluated by the WOMAC pain sub-score. The power calculation is based on data from a 4-week double-blind diclofenac sodium 2 % topical solution treatment study in knee osteoarthritis patients (Wadsworth et al. 2016). In this study using the WOMAC LK (Likert) 3.1 scale (0-4 for each question), a decrease from baseline in WOMAC pain sub-score (5 questions) was recorded in the diclofenac treatment group of 4.5 (SD 4.5) and in the placebo group 3.6 (SD 4.2).

The estimated common SD of 4.4 in the LK 3.1 scale can be converted to a SD of 4.4 \* 2.5 = 11 in the NRS scale. Calculations based on a series of assumptions are shown below in Table **2**. With the assumptions of the SD of 11 (NRS scale), 120 subjects enrolled in each of the double-blinded treatment arms, 10 % dropout rate, normal distribution, 5 % level of significance two-sided, 80 % power, the study will be powered to detect a treatment difference in WOMAC pain sub-score between AMZ001 BID and placebo of 4.2 on the NRS scale.

WOMAC pain-subscore difference	Common SD	Power
3.8	9	0.87
	11	0.72
	13	0.57
4.0	9	0.90
	11	0.76
	13	0.61
4.2	9	0.93
	11	0.80
	13	0.66

Table 2 Power calculations for pairwise difference in WOMAC pain sub-score between AMZ001 andplacebo with 108 evaluable subjects per group, 5 % level of significance, two-sided.

The power is not adjusted for multiple comparisons and adjustment for multiplicity will not be made as there is one test only performed for the primary endpoint.

It should be noted that the current trial is not designed or powered to evaluate superiority of AMZ001 compared to Voltaren® gel, but the trial will provide important information on onset and duration of action of AMZ001 to guide future, larger trials. Also, the trial is not powered to evaluate superiority of AMZ001 applied twice daily as compared to once daily, but the trial will provide information on efficacy, safety, and tolerability of twice daily administration as compared to once daily administration.

Furthermore, the trial will be used to finalize the psychometric validation of the Pain Diary and the Satisfaction Questionnaire.

## 2.3 Blinding

This is a double-blind study of AMZ001 (QD and BID regimens) versus placebo, which also includes a single-blind active comparator (Voltaren® gel 1 %).

Due to lack of availability of Voltaren® gel 1 % in metered dose-dispensers identical to that of the double-blinded IMP, as well as due to differences in approved daily dose application schedules, full masking of Voltaren® gel 1 % was not considered feasible for this trial. Instead, the Voltaren® gel 1 % is single-blinded to conceal the brand of the product. The single-blinded product is labelled identically to other IMPs in the trial. All double-blinded IMPs will be indistinguishable in appearance of the container, the label, as well as the gel appearance, smell and texture. The appearance of the single-blinded Voltaren® gel tube will be masked to fully cover any branding information.

Neither subject, investigator nor staff working on the study will be aware of treatment allocation to the double-blind treatment groups. The dispensation type (metered dose-dispenser vs. gel tube) and required frequency of application risks unblinding of the allocation of Voltaren® gel for the subjects allocated to the single-blinded treatment groups. Due to the difference in primary packaging material, study staff will be indirectly unblinded to allocations to the Voltaren® gel treatment group.

As the primary efficacy data analyses will be performed on the double-blinded treatment groups, the risk of bias associated with single-blinded treatment groups is considered irrelevant to the main data output.

All summaries produced before database lock will be presented using dummy treatments and this will be explicitly stated.

## 2.4 Randomization

The screening/randomization procedure will be centrally managed through an electronic Interactive Web Responding System integrated in the eCRF.

Eligible subjects will be randomized to one of four treatment groups with an allocation ratio of 3:3:3:2. Each of the three double-blinded treatment groups (AMZ001 BID, AMZ001 QD and placebo) will be randomized with approximately 120 subjects for the primary objective of assessment of an analgesic effect of topical AMZ001 gel compared with placebo. The single-blinded group of the comparator of Voltaren® gel 1 % will be randomized with approximately 80 subjects.

Randomization will be stratified by country to ensure balance of treatment groups with respect to intrinsic and extrinsic factors that may affect the OA outcomes.

# 3 Analysis sets

Every subject will be classified according to the below definitions of the Intention-to-Treat (ITT), Modified Intention-to-Treat (mITT), Per-Protocol (PP) and Safety (SAF) analysis sets at the Blind Data Review Meeting before breaking the blind. The decisions will be made by the trial team and documented in the minutes of the meeting.

Outputs on demographics and baseline characteristics, medical history, prior medication and concomitant medication will be performed using the ITT, mITT, PP and SAF analysis sets. Subject disposition will be summarized for all screened subjects and protocol deviations will be summarized for the ITT analysis set. Exposure and compliance will be performed using the ITT and SAF analysis sets.

# 3.1 Intention-to-Treat Analysis Set (Full analysis set)

The ITT analysis set will include all subjects randomly allocated to a treatment, based on the intention to treat "as randomized" principle (i.e. the planned regimen rather than the actual treatment given in case of any difference).

# 3.2 Modified Intention-to-Treat analysis set

The mITT analysis set will include all subjects from the ITT analysis set who have a baseline and at least one post-treatment WOMAC pain sub-score assessment available.

The mITT analysis set will be used to perform all efficacy analyses and summaries. Subjects will be analysed according to the randomized treatment.

# 3.3 Per-protocol analysis set

The PP analysis set will include all subjects from the mITT analysis set who have been treated according to the trial protocol and fulfil the following criteria:

- Absence of major clinical trial protocol deviations with respect to factors likely to affect the efficacy of the treatment, where the nature of such clinical trial deviations will be defined before breaking the blind. Major protocol violations could include although not limited to major deviations of inclusion/exclusion criteria and use of prohibited medication.
- Adequate compliance with trial medication; defined as overall compliance of the target knee

between 75% and 125%.

The PP analysis set will be used to perform sensitivity analyses for the primary endpoint.

### 3.4 Safety analysis set

The SAF will include all subjects who have taken at least one application of trial treatment. Subjects will be analysed according to the actual treatment they receive.

The actual treatment received by each subject will be established by the unblinded data-manager. At the Blind Data Review Meeting, the unblinded data-manager will present a **subject blinded** list of treatment misallocations for review. For subjects misallocated treatment, the actual treatment received will be decided based on below categories and documented. For subjects receiving treatment as per the randomization, actual treatment is identical to planned treatment.

Since dispensation of IMP occurs at multiple timepoints (Visit 2, Visit 4 and as needed), subjects will fall into one of the following three actual treatment categories:

- 1. IMP is dispensed correctly on all occasions.
- 2. IMP is consistently dispensed incorrectly on all occasions i.e. the subject received the same (incorrect) treatment throughout the study and the IMP received corresponds to one of the study treatment groups.
- 3. IMP is dispensed incorrectly on one or more occasions and the subject did not consistently receive IMP corresponding to one of the study treatment groups.

In order not to bias the safety reporting of the study treatment groups, any subjects falling into category 3 above will be included in the SAF under a separate treatment group 'AMZ – misallocations' and will therefore not be included in the safety summaries for any of the study treatment groups.

The SAF will be used for all safety and tolerability summaries.

# 4 Statistical analyses and presentation of data

### 4.1 General considerations

Descriptive summaries and analyses when applicable will be presented for the following treatment groups: AMZ001 BID, AMZ001 QD, Placebo and Voltaren 1%.

### 4.1.1 Data presentation

All statistical tests will be performed using a two-sided test at a 5% significance level. Results from analyses will be presented with estimates, 95% confidence intervals (CIs) and p-values.

Numerical data will be presented in summary tables by number of observations (n), the number of missing values (missing), arithmetic mean, standard deviation (SD), median, first and third quartiles (Q1, Q3), minimum (min) and maximum (max) values. The mean, median, Q1 and Q3 will be reported to one decimal place more than the raw data, the standard deviation to two decimal places more than the raw data and the minimum and maximum values to the same precision as the raw data. The summary statistics presented for categorical data will be the

number of observations (n), the number of missing values (missing) and the count and percentage of subjects in each category. Number of events will also be reported where applicable.

All data will be listed by treatment group, subject and time point (if applicable). Age and sex will be displayed in all listings.

## 4.2 Efficacy

### 4.2.1 **Primary efficacy analysis**

The primary efficacy analysis will include data from the double-blind treatment groups only.

### 4.2.1.1 Derivation of primary endpoint

The primary endpoint is the change from baseline at week 4 in the WOMAC pain sub-score in the target knee.

The WOMAC pain sub-score is derived from WOMAC Osteoarthritis Index questionnaire as the sum of questions 1 to 5. It takes values in the range 0-50, where higher values indicate greater pain. For convenience and ease of interpretation, all WOMAC scores (including the pain sub-score) will be normalised to a 0-100-point scale for data analysis.

For the primary endpoint,

normalised WOMAC pain sub-score = (WOMAC pain sub-score/50) \* 100

The full WOMAC questionnaire is assessed for the target knee at baseline (Visit 2), week 1 (Visit 3) week 2 (Visit 4), week 3 (Visit 5) and week 4 (Visit 6).

### 4.2.1.2 Summary presentations and method of analysis

The absolute values and the absolute change from baseline in the WOMAC pain sub-score will be summarized over time by treatment group.

The primary analysis will use a restricted maximum likelihood based repeated measures mixed model (MMRM) on the dependent variable absolute change from baseline of the WOMAC pain sub-score. The analysis will include covariates of baseline value (WOMAC pain sub-score), treatment, timepoint, sex, country, the subject characteristic of unilateral/bilateral knee OA at baseline (defined by whether one or both knees meet the requirements for target knee selection) and treatment-by-timepoint interaction. An AR(1) covariance structure will be used to model the correlations between within-subject repeated measurements. The Kenward-Roger approximation will be used to estimate denominator degrees of freedom and adjust standard errors.

Sample SAS code to be used for the MMRM analysis:

```
proc mixed data=;
class treatment visit sex status subject;
model response = treatment visit treatment*visit sex country status baseline / ddfm=kr s;
repeated visit / subject=subject type=ar1;
lsmeans visit*treatment / diffs cl obsmargins;
```

run;

where *response* is the change from baseline in WOMAC pain sub-score and *baseline* is the WOMAC pain sub-score at baseline, *status* is the categorical variable of either unilateral or bilateral knee OA at baseline and *visit* is the study timepoint.

Least square mean estimates of change from baseline in WOMAC pain sub-score along with 95% confidence intervals (CI) will be presented at each time-point for each treatment group.

Estimated treatment differences at week 4 between all treatment groups along with associated 95% confidence intervals and p-values will be presented. P-values will be interpreted according to the hierarchical step-down testing procedure specified for the primary objective and also with consideration as to whether they are secondary or exploratory objectives. Model-estimated least square means and associated 95% CI of change from baseline in WOMAC pain sub-score will be plotted over time by treatment group.

The primary efficacy analysis will be based on the mITT. The robustness of the results of the primary analysis will be investigated by a sensitivity analysis based on the PP.

Further investigation of the robustness of the primary results (in particular, the influence of time and covariates) may be performed, if deemed necessary.

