**Diagnosis and inclusion and exclusion criteria:****Inclusion Criteria:**

1. Subject is able to read and understand the language and content of the study material, understand the requirements for study visits, and is willing to provide information at the scheduled evaluations and appropriate written informed consent has been obtained.
2. Femorotibial osteoarthritis of the knee, according the American College of Rheumatology (ACR) clinical and radiographic criteria (Altman et al. 1986) (Appendix A).
3. Radiological OA grade 1, 2, or 3 of the target knee, using the Kellgren-Lawrence method (KELLGREN & LAWRENCE 1957) as graded by central, independent reading of X-ray obtained during screening, or on a recent (within 6 months) X-ray image which fulfills the specifications for central reading.
4. Age between 40 years and 85 years at the time of screening, both included; of either sex.
5. Pain score rated on an 11-point numerical rating scale of the target knee of  $\geq 20$  and  $\leq 45$  out of 50 in response to the WOMAC pain sub-score (5 questions), at the time of screening. The subject should have undergone a washout-period of at least 5 half-lives of any analgesic medication before completing the screening questionnaire.
6. Women of child-bearing potential must use at least an acceptably effective method of contraception (progestogen-only oral hormonal contraception, where inhibition of ovulation is not the primary mode of action, male or female condom with or without spermicide, cap, diaphragm or sponge with spermicide). Postmenopausal status is defined as being amenorrheic for at least 1 year prior to screening. Sexually active men with a female partner of childbearing potential must agree to use condom from enrolment up to at least 3 months after the study end.
7. Knee pain in the target knee for 14 days of the preceding month (periarticular knee pain due to OA and not due to non-OA conditions such as bursitis, tendonitis, etc.) based on subject report.
8. On stable pain therapy (i.e., at least 3 days per week for the previous month) with an oral NSAID, or acetaminophen/paracetamol prior to the Screening Visit.
9. Except for osteoarthritis, the subject is in reasonably good health as determined by the Investigator.

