#### 4.2.2.1 Secondary endpoints

#### **WOMAC Osteoarthritis Index**

The WOMAC Osteoarthritis Index consists of 24 questions about aspects of the target knee over the previous 24 hours. The questions are split into three sections: *Pain, Stiffness* and *Difficulty Performing Daily Activities* (i.e. Physical Function). Each question is scored on a 0-10 11-point numerical scale, where higher numbers indicate greater pain, stiffness or difficulty in performing daily activities.

WOMAC scores	Range (min – max)	Derivation
Total score	0 - 240	Q1 + Q2 + + Q23 + Q24
Pain sub-score	0 - 50	Q1 + Q2 + Q3 + Q4 + Q5
Pain weight bearing sub-score	0 - 30	Q1 + Q2 + Q5
Pain non-weight bearing sub-score	0 - 20	Q3 + Q4
Stiffness sub-score	0 - 20	Q6 + Q7
Function sub-score	0 - 170	Q8 + Q9 + + Q23 + Q24

The following scores are derived from answers to the WOMAC questionnaire:

For convenience and ease of interpretation, all WOMAC derived scores will be normalised to a 0-100-point scale for data analysis where, for each score

#### normalised score = (score/max possible value) \* 100

The full WOMAC questionnaire is assessed for the target knee at baseline (Visit 2), week 1 (Visit 3) and weeks 2, 3 and 4.

The WOMAC pain sub-scale is also completed at screening for both the left/right hips and the left/right knees. This is for the assessment of baseline status and eligibility, the determination of the target knee and whether the subject has bilateral or unilateral knee OA.

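### Adding the target-knee screening pain score as a second covariate in the primary model would be a free but modest precision gain, about 0% to 4% of week-4 residual variance

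*SAP*

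**What the plan says.** SAP 4.2.1.2 specifies the primary MMRM: "The analysis will include covariates of baseline value (WOMAC pain sub-score), treatment, timepoint, sex, country". The remaining terms are unilateral/bilateral knee OA at baseline and treatment by timepoint. The sample MODEL statement agrees with the text and has a single pain term, the baseline value. SAP 4.2.1.1 places baseline at Visit 2. The statistical methods in the protocol synopsis also name only the baseline value.

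The screening measurement is described under the WOMAC heading of SAP 4.2.2.1: "The WOMAC pain sub-scale is also completed at screening for both the left/right hips and the left/right knees". Its stated uses there are baseline status, eligibility, choice of target knee and unilateral/bilateral classification. Inclusion criterion 5 requires a target-knee score of 20 to 45 out of 50 at screening and adds: "The subject should have undergone a washout-period of at least 5 half-lives of any analgesic medication before completing the screening questionnaire". The schedules in both documents put this score at Screening 1b (Day -13 to -1) and the baseline score at Visit 2 (Day 1). A footnote to the WOMAC row asks for five analgesic half-lives of washout at each assessment.

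**The concern.** The endpoint is measured twice before treatment, on different days and under the same washout condition, and the model uses one of the two as a continuous covariate. WOMAC items refer to the previous 24 hours, so a single score carries day-to-day noise. A second reading of the same quantity may predict week 4 beyond what Visit 2 already explains. It is measured before randomisation, so adjusting for it does not bias the treatment comparison.

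What is at stake is precision only. SAP Table 2 leaves little margin on its own terms: 0.80 at a difference of 4.2 and SD 11, but 0.72 if the difference is 3.8 and 0.66 if the SD is 13. A covariate already collected is therefore worth considering, provided its likely yield is stated realistically.

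**Working it through.** **Inputs from SAP 2.2 and 4.1.1.** Tests: "All statistical tests will be performed using a two-sided test at a 5% significance level". Sample size: "120 subjects enrolled in each of the double-blinded treatment arms, 10 % dropout rate", hence 120 × 0.9 = 108 evaluable per arm. Target: "treatment difference in WOMAC pain sub-score between AMZ001 BID and placebo of 4.2 on the NRS scale". SD: 4.4 × 2.5 = 11 on the 0-50 sum, derived from reported changes from baseline, so it is an SD of change before covariate adjustment.

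**The plan's own figure.** With 108 per arm, difference 4.2 and SD 11, power is 0.801 (normal) or 0.798 (noncentral t). The stated 0.80 reproduces, as do all nine cells of Table 2 within 0.01.

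**Assumptions (not in the documents).** Trivariate normal scores at screening, Visit 2 and week 4; mean 27; SD 9, 9 and 11; subjects kept only if the screening score is 20 to 45. A week-4 ANCOVA stands in for the MMRM. Correlations are varied.

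**Formulas.** Let r = corr(Visit 2, week 4), s = corr(screening, week 4) and q = corr(screening, Visit 2), all after truncation.
- R² with both scores = (r² + s² − 2rsq)/(1 − q²)
- Variance ratio = (1 − R²)/(1 − r²)
- SD of change before truncation = √(81 + 121 − 2 × correlation × 99)

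**Worked case, all correlations 0.4 before truncation.** SD of change = √(202 − 79.2) = 11.08 (11.07 after truncation), which matches the SAP. After truncation r = 0.343 and s = q = 0.283. R² = (0.1176 + 0.0801 − 0.0549)/0.9199 = 0.155. Variance ratio = 0.845/0.882 = 0.957, a cut of 4.3%. Equivalent subjects: 108 × (1/0.957 − 1) ≈ 4.8 per arm. Residual SD goes from 9.88 to 9.67 and power (noncentral t) from 87.5% to 88.9%.

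**Equal correlations across the range**

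| Correlation | SD of change | Variance cut | Power, Visit 2 only → both |
|---|---|---|---|
| 0.4 | 11.1 | 4.3% | 87.5% → 88.9% |
| 0.5 | 10.1 | 6.2% | 91.2% → 92.8% |
| 0.6 | 9.1 | 8.5% | 95.0% → 96.5% |
| 0.7 | 7.9 | 11.3% | 98.1% → 99.0% |

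Only the first row agrees with an SD of change of 11.

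**Screening and Visit 2 more alike (correlation 0.7)**

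| Visit 2-week 4 | Screening-week 4 | Variance cut |
|---|---|---|
| 0.5 | 0.5 | 3.7% |
| 0.4 | 0.4 | 2.1% |
| 0.5 | 0.4 | 0.4% |
| 0.4 | 0.28 (= 0.4 × 0.7) | 0% |

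**Sensitivity to the assumed spread.** With SD 11 at all three times, mean 28 and equal correlations of 0.5, the SD of change is again 11.0 and the cut is 5.0% (108 × 0.050 = 5.4 subjects). With SD 9 before treatment, 12 at week 4 and equal correlations of 0.5, the SD of change is √(81 + 144 − 108) = 10.8 and the cut is the 6.2% of the 0.5 row, because the cut does not depend on the week-4 SD. So 4% is not a sharp ceiling.

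**The case against.** The strongest reply is that nothing here is wrong. Adjusting for the baseline value is standard practice, the estimate is unbiased, and the protocol names only that covariate. The documents give no correlations, so a material gain is not shown. Equal correlations are also the favourable case: screening and Visit 2 are both untreated and may be only days apart, while week 4 comes four weeks later on treatment, so the two early scores may largely duplicate each other. Under correlation that decays with time, in the spirit of the AR(1) structure the SAP chose, the gain is 0% to 3%. All of this stands, and it limits the point to an optional efficiency improvement.

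A reader might infer more than the documents support:
- **That power would rise from 80% to 84%, worth about 14 subjects per arm.** This pairs the 11.3% cut, which needs correlations of 0.7, with a residual SD of 11. At the assumed spreads, correlations of 0.7 imply an SD of change of 7.9. The SAP's 11 is the unadjusted SD of change, not the residual SD after Visit 2 adjustment.
- **That the covariate can only help.** If screening adds nothing beyond Visit 2, one degree of freedom is spent for no return, although that loss is negligible with more than 300 subjects.
- **That no missing values can arise.** Criterion 5 secures the score for every eligible subject, but SAP 3.2 admits to the mITT set anyone with a baseline and one post-treatment score, and SAP 3.3 anticipates major eligibility deviations.
- **That the screening score is discarded.** It determines eligibility, target knee and unilateral/bilateral status, and the last of these is a model term.

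**Conclusion.** The point holds as a modest improvement, not as an error. The primary model omits a second continuous pre-randomisation measure of its own endpoint, and including it costs almost nothing. On assumptions that fit the SAP's SD of change of 11 (SD 9 before treatment, 11 at week 4, screening restricted to 20-45), the residual variance at week 4 falls by about 0% to 4%. That is at most about 5 evaluable subjects per arm and about 1 to 1.5 power points at the upper end, from a base already above 80% because the Visit 2 adjustment is itself worth several points. Wider assumed spreads take the cut to 5% or 6%. The result rests on assumed correlations and normal scores, and the gain is nil if the screening score carries no information beyond Visit 2.

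**What to change.** Before unblinding, amend SAP 4.2.1.2:
- Add the target-knee screening WOMAC pain sub-score as a second continuous covariate, in the text and in the MODEL statement.
- Keep Visit 2 as baseline and change from Visit 2 as the response. Screening scores are restricted by the entry limits and may be inflated near the cut-off, so the model should estimate their weight.
- State a simple rule for any mITT subject enrolled in deviation without a screening score, for example imputing the overall mean, so that nobody drops out of the primary analysis.

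The cost is one covariate, one sentence on missing values and one degree of freedom, with no new data collection. SAP 4.2.1.2 already allows optional later work on the influence of covariates, but that cannot support the primary p-value in the way a pre-specified term can.
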